### 12.8.2 Introduction

Hepatotoxicity is injury or damage to the liver that may be associated with impaired liver function (Navarro and Senior 2006). Drug-induced hepatotoxicity is one of the most common causes of termination of drug development, a major reason for refusal of market authorization and for restricted use, and the single most important cause of the withdrawal of market authorization for products (Björnsson 2006). Thus, drug-induced hepatotoxicity is a major concern during the discovery, development to post-authorization phases of the product life cycle (excerpted from Draft Guidance Document, Hepatotoxicity of Health Products, Ministry of Public Health, Canada, December 2010).

As stated in the United States Food and Drug Administration (FDA) “Guidance for Industry - Drug-Induced Liver Injury: Premarketing Clinical Evaluation”; hepatocellular injury (usually detected by serum aminotransferase elevations [AT]) can be caused by drugs that rarely, if ever, cause severe DILI (e.g., aspirin, tacrine, statins, and heparin), as well as by drugs that do cause such injury. The frequency of serum AT elevations also is not a good indicator of a potential for severe DILI because drugs such as tacrine (not a cause of severe DILI) can cause AT elevations in as many as 50 percent of subjects. Very high levels of observed ATs may be a somewhat better indicator of potential for severe DILI, but the most specific indicator is evidence of altered liver function accompanying or promptly following evidence of hepatocellular injury.

The single clearest (most specific) predictor found to date of a drug’s potential for severe hepatotoxicity, is the occurrence of hepatocellular injury (AT elevation) accompanied by increased serum total bilirubin (TBL) not explained by any other cause, such as viral hepatitis or exposure to other hepatotoxins, and without evidence of cholestasis, together with an increased incidence of AT elevations in the overall trial population compared to control. Increased plasma prothrombin time, or its international normalized ratio (INR), a consequence of reduced hepatic production of Vitamin K-dependent clotting factors, is another potentially useful measure of liver function that might suggest the potential for severe liver injury.

Recognition of the importance of altered liver function, in addition to liver injury, began with Hyman Zimmerman's observation that drug-induced hepatocellular injury (i.e., AT elevation) accompanied by jaundice (i.e., TBL elevation) had a poor prognosis, with a 10 to 50 percent mortality from acute liver failure (in pretransplantation days) (Zimmerman 1978, 1999). This became known as "Hy's Law". This document describes the recommended process for monitoring and evaluation of subjects meeting the laboratory criteria for potential DILI defined as:

- an elevated alanine transaminase (ALT) or aspartate transaminase (AST) lab value that is greater than or equal to three times (3X) the upper limit of normal (ULN) and
- an elevated TBL lab value that is greater than or equal to two times (2X) ULN and
- at the same time, an alkaline phosphatase (ALP) lab value that is less than 2X ULN,

as a result of within-protocol-specific testing or unscheduled testing.

The protocol identifies these laboratory criteria for potential DILI as ECIs. ECIs are selected adverse experiences that must be reported to the Sponsor within 24 hours. The Principal Investigator should record these ECIs on the Adverse Experience Case Report Forms (CRFs) and complete pertinent adverse experience fields as outlined in the Data Entry Guidelines (DEGs).

### 12.8.3 Close Observation Recommendations

The following steps should be taken when a subject is observed to have an elevated AST or ALT lab value that is greater than or equal to 3X ULN and an elevated TBL lab value that is greater than or equal to 2X ULN and, at the same time, an ALP lab value that is less than 2X ULN, as a result of within-protocol-specific testing or unscheduled testing. In addition, close monitoring of *isolated* bilirubin increases greater than 2X ULN will be required.

Initiate **close observation**, defined below, and continue performing **follow-up to resolution**.

**Close observation is defined as follows:**

- Repeat liver enzyme and serum bilirubin tests two (2) or three (3) times weekly. Frequency of retesting can decrease to once a week or less if abnormalities stabilize or study drug has been discontinued and the subject is asymptomatic.
  - For subjects with *isolated* bilirubin elevations greater than 2X ULN, repeat serum bilirubin tests every 2 weeks until the bilirubin returns to normal or baseline.
- Obtain a more detailed history of symptoms and prior or concurrent diseases (see 12.8.5).
- Obtain a history of concomitant medication use (including prescription and nonprescription medications, herbal and other dietary supplements), alcohol use, recreational drug use and special diets (see Section 12.8.5 for details).
- Obtain a history of exposure to chemical agents or other environmental toxins.

- Obtain additional history and complete Stage 1 work-up to attempt to rule out other potential causes of the transaminase elevation, including but not limited to the following: acute viral hepatitis types A, B, C, D, and E; autoimmune or alcoholic hepatitis; non-alcoholic steatohepatitis (NASH); hypoxic/ischemic hepatopathy; and biliary tract disease (see Section 12.8.5 for details).
- Consider gastroenterology or hepatology consultation.

**In general, treatment with study therapy should be stopped if the laboratory criteria for potential DILI are met. Please refer to the specific discontinuation criteria in the protocol as appropriate.**

#### 12.8.4 Hepatic Assessment Flow Chart

[figure not shown]

Figure 4 Hepatic Assessment Flow Chart

#### Factors to Consider in Assessing Potential DILI

When there is a potential DILI, it is important to thoroughly assess the subject's history, hepatic risk factors, clinical condition and hepatic function until resolution (normal or baseline levels).

Answers to the following questions should be recorded in source documents and in appropriate CRFs as outlined in the DEGs.

##### 12.8.4.1 Study Medication

Considerations should include the following: What was the time interval between administration of study medication and the laboratory abnormality(ies)? What is the status of study medication use: Continuing? Interrupted? Discontinued? Was the subject re-challenged with study medication?

#### 12.8.4.2 Treatment

Record any concomitant treatments.

#### 12.8.4.3 Signs and Symptoms (associated with the potential DILI event)

Does the subject have a concomitant illness? Does the subject currently exhibit signs or symptoms of hepatitis/DILI? What are the subject's signs and symptoms (see examples below)? What are the pertinent findings from medical history, physical/laboratory examination (e.g., fatigue, nausea, vomiting, right upper quadrant pain or tenderness, fever, rash, and/or eosinophilia > 5%, hepatomegaly, splenomegaly, etc.) that could suggest DILI?

Category	Examples of Signs and Symptoms
Blood/lymphatic	Eosinophilia, coagulopathy, susceptibility to bleeding/bruising
Circulatory	Varicose veins, edema
Constitutional	Fever, fatigue, malaise, weight gain, other (identify).
Digestive/hepatic	Anorexia, diarrhea, bloody or black stool, light-colored stools, nausea, vomiting, hematemesis, upper quadrant abdominal pain, upper quadrant tenderness, hepatomegaly, jaundice, splenomegaly, ascites, cholestasis
Endocrine/reproductive	Loss of libido
Integumentary	Rash, pruritus
Muscular	Myalgia
Nervous	Changes in mental status or level of consciousness
Urinary	Dark urine

#### 12.8.4.4 Confounding Variables

What are the relevant medical history and findings? What is the differential diagnosis? What risk factors does the subject have for hepatic injury? (See examples below.) Provide onset of risk factor and duration.

Category	Examples of Confounding Variables
Subject medical history	Autoimmune disorder, cancer, Gilbert's syndrome, obesity, Wilson's disease
Substance use/abuse	Alcohol, illegal drugs, illegal intravenous (IV) drugs
Prior & Concomitant Medications: Review all non-study medications and therapies, including: over-the-counter (OTC), as well as prescription. Ask the subject to bring products/packaging to site and review contents.	History of recent concomitant acetaminophen (APAP)/paracetamol use, excessive nonsteroidal anti-inflammatory drug (NSAID) intake, use of non-study drug or therapy that can cause liver damage or idiosyncratic adverse drug reactions
Herbal and nutritional supplements	Herbal, complementary therapies, and nutritional supplements
Adulteration of products	History of previous exposure to the product or a similar product, and information on potential contamination or adulteration of products
Chemical exposure	Occupational or in other situations
Potential exposure to infectious agents	Infectious hepatitis, transfusion, travel, tattoos, sexually transmitted diseases, new sexual partner, shared needles
Special Diet	Special diet started since randomization
Other	Recent physical trauma, excessive exercise, or other prolonged physical exertion
Family history	Autoimmune disorder, cancer, Gilbert's syndrome, Wilson's disease

#### 12.8.4.5 Evaluation Algorithm for Potential DILI if there are No Other Clinical Reasons

Note: If clear etiology for the laboratory abnormalities has been confirmed, Stage 1 and 2 testing may not be required. In this case, consultation with the Sponsor is recommended.

**Stage 1 work-up should be performed within 48-72 hours:**

- ALT
- AST
- Bilirubin: total, direct, indirect
- Alkaline phosphatase (ALP)
- Prothrombin Time (PT)/international normalized ratio (INR)
- Creatine phosphokinase (CPK)
- Manual eosinophil count (if automated count was elevated)
- Toxicology screen for drugs of abuse (including ethanol) and for acetaminophen/paracetamol level should also be sent. Investigators may order additional toxicology tests as clinically indicated.
- Evaluate subject for the following signs and symptoms: fatigue, nausea, vomiting, right upper quadrant abdominal pain or tenderness, fever, rash.
- Obtain the following additional history and assessment for associated risk/confounding factors:
  - More detailed history of symptoms and prior or concurrent illness
  - Aminotransferase values obtained prior to the study or administration of study medication
  - Alcohol consumption (recent and historical)
  - Acetaminophen (APAP)/paracetamol use
  - New prescription, concomitant, or non-prescription (including herbal and other dietary supplements) medications
  - Unusual foods (e.g. mushrooms) or special diets. Consumption of seasonal foods.
  - Recreational drug use
  - Prior history of liver injury or disease, including but not limited to Gilbert's syndrome, autoimmune disorders, cancer, Wilson's disease, NASH, alcoholic or infectious hepatitis, biliary tract disease, hypoxic/ischaemic hepatopathy
  - Obesity/abdominal adiposity (record weight, height, and waist circumference)
  - Occupational history and history of exposure to chemical agents or other environmental toxins
  - Recent travel (last three [3] years)

- Transfusion history
- Perform the following required laboratory tests:
  - Albumin
  - Eosinophils (percentage and absolute; obtain manual count if automated count is elevated)
  - Viral hepatitis serologies (obtain appropriate consent prior to testing, if required locally)
    - A (IgG, IgM)
    - B (HepBs Ag, Hep Bs Ab, Hep Bc Ab, Hep Be Ag)
    - C (RNA)
    - D (requires concomitant hepatitis B infection)
  - Human Immunodeficiency Virus (HIV) testing (obtain appropriate consent prior to testing, if required locally)
  - Evaluation for autoimmune hepatitis:
    - Serum gamma globulin levels/ serum protein electrophoresis
    - Antinuclear antibody (ANA)
    - Anti-mitochondrial antibody (if ALP or TBL >ULN)
  - If AST/ALT ratio is greater than one (1) with suspicions of increased alcohol intake, perform the following:
    - Gamma-glutamyl transferase (GGT)
- Obtain a right upper quadrant ultrasound

**Stage 2 work-up tests should be drawn within one (1) week of receiving the Stage 1 work-up results and the results of Stage 1 evaluation are negative.**

**Note: A specific test may be performed earlier if the investigator determines that the clinical presentation leads to a certain diagnosis.**

**Stage 2 work-up:**

- Perform the following laboratory tests:
  - Genetic test for Gilbert's disease if there is a suspicious history. Ensure appropriate subject consent is obtained for this test.
  - Viral hepatitis E (IgG and IgM, obtain appropriate consent prior to testing, if required locally)
  - Anti-smooth muscle antibody
  - Anti-liver-kidney microsomal antibody
  - Anti-soluble liver antigen

- Serologies for the following:
  - Cytomegalovirus (CMV) (IgG, IgM)
  - Epstein-Barr Virus (EBV) (IgG, IgM)
  - Herpes simplex
  - Toxoplasmosis
  - Varicella
  - Parvovirus
- Ceruloplasmin
- Serum alpha-1 anti trypsin
- Genetic test for hemochromatosis. Ensure appropriate subject consent is obtained for this test
- Iron Studies:
  - serum ferritin,
  - serum iron,
  - total iron binding capacity
- Consider referral to hepatologist/gastroenterologist
- Consider screen for celiac disease and cystic fibrosis if clinically indicated
- If laboratory tests or ultrasound evidence of biliary tract obstruction, consider obtaining Endoscopic Retrograde Cholangiopancreatography (ERCP) or Magnetic Resonance Cholangiopancreatography (MRCP)

If applicable, request copies of hospital discharge summaries, consultation reports, pathology reports, special studies (e.g. imaging or biopsy), etc.

#### 12.8.4.6 Potential Diagnosis

What diagnosis do the history, clinical course, and laboratory tests suggest?

#### 12.8.4.7 Overall Clinical Impression

What are the investigator's overall clinical impressions (e.g., differential diagnosis, potential alternative causes)?

#### 12.8.4.8 Treatment Plan

What is the plan for treatment and follow-up?

## 12.9 Non-Exhaustive List of Drugs and Substances with the Potential to Interfere with CYP3A4 and CYP2A6

**Strong CYP3A4 interfering agents are prohibited (in bold and underlined).**

A **strong inhibitor** increases the AUC of a substrate for a given CYP by  $\geq$  5-fold or  $>$  80% decrease in clearance. A **strong inducer** decreases the AUC of a substrate for a given CYP by  $\geq$  80%.

Strong CYP3A4 inducers	Strong CYP3A4 inhibitors		Moderate CYP3A4 inducers	Moderate CYP3A4 inhibitors	
avasimibe	boceprevir	nefazodone	amobarbital	atazanavir	fluconazole
carbamazepine	clarithromycin	nelfinavir	dexamethasone	amiodarone	fosamprenavir
phenytoin	conivaptan	posaconazole	efavirenz	amprenavir	imatinib
rifampicin	grapefruit juice 	ritonavir	felbamate	aprepitant	miconazole
St John's wort 	indinavir	saquinavir	nevirapine	cimetidine	suboxone
	itraconazole	telaprevir	omeprazole	cyclosporine	verapamil
	ketoconazole	telithromycin	phenobarbital	darunavir	
	lopinavir	tipranavir	pioglitazone	delavirdine	
	mibepradil	voriconazole	primidone	diltiazem	
			rifabutin	erythromycin	
			tamoxifen		
			troglitazone		
CYP3A Sensitive substrates				CYP3A Substrates with a Narrow Therapeutic Range	
alfentanil	dronedarone	lovastatin	simvastatin	alfentanil	fentanyl
aprepitant	eletriptan,	lurasidone	sirolimus	astemizole	pimozide
budesonide	eplerenone,	maraviroc	tolvaptan	cisapride	quinidine
buspirone	everolimus	midazolam	tipranavir	cyclosporine	sirolimus
conivaptan	felodipine	nisoldipine	triazolam	dihydroergotamine	tacrolimus
darifenacin	indinavir	quetiapine	vardenafil	ergotamine	terfenadine
darunavir	fluticasone	saquinavir			
dasatinib	lopinavir	sildenafil			
CYP2A6 inducers	CYP2A6 inhibitors		Other CYP2A6 substrates		
phenobarbital	grapefruit juice		coumarin		
rifampicin	ketoconazole		nicotine		
	methoxsalen		halothane		
	pilocarpine		quinoline		
	tranylcypromine		losigamone		
	SM-12502		SM-12502		
	valproic acid		valproic acid		

1. Preparation-dependent

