#### 4.1.1.2 MK-8628 Metabolism – CYP Interactions

Results from MK-8628 incubations either with individual recombinant CYPs or with human microsomes and chemical inhibitors to individual CYPs show MK-8628 was metabolized to the mono-hydroxylated metabolite mainly by CYP3A4 and to a lesser extent by CYP2C9 and potentially by CYP2C19, which will need to be confirmed. Results from incubations with individual UDP glucuronosyltransferase(s) (UGT) showed that MK-8628 can be glucuronidated mainly by UGT1A7 and, to a lesser extent, by UGT1A1, 1A10, 1A3, 1A8, and 1A9. MK-8628 inhibits CYP2A6 and 3A4 turnover of probe substrates in microsomes with IC50 values that were >10 μM. At 10 μM MK-8628, the inhibition of CYP2A6 and CYP3A4 were 30% and 39%, respectively. MK-8628 has a high apparent permeability (Papp)

$\geq 21 \times 10^{-6}$  cm/s apical-to-basal) across cell monolayers and is a P-gp substrate. The involvement of several enzymes in the metabolism of MK-8628 reduces concerns for victim drug-drug interaction (DDI). The inhibition of CYP2A6 and particularly CYP3A4 raises concerns that MK-8628 could be a perpetrator in a DDI with co-administered drugs whose clearance is primarily mediated by these enzymes.

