### 5.1.3 Subject Exclusion Criteria

The subject must be excluded from participating in the trial if the subject:

1. Has participated in another clinical trial or treatment with any investigational drug (excluding anticancer treatments) within 30 days prior to study entry.
2. Has other concomitant anticancer treatment.
3. Has persistent grade  $>1$  clinically significant toxicities related to prior antineoplastic therapies (except for alopecia); stable sensory neuropathy  $\leq$  grade 2 NCI-CTCAE v. 4.0 is accepted.
4. Has a known additional malignancy that is progressing or requires active treatment. Exceptions include basal cell carcinoma of the skin, squamous cell carcinoma of the skin, or in situ cervical cancer that has undergone potentially curative therapy.
5. Has taken a similar class of therapy previously (BET inhibitor).
6. Has inability to swallow oral medications or presence of a gastrointestinal disorder (e.g. malabsorption) deemed to jeopardize intestinal absorption of MK-8628.

7. Has known primary CNS malignancy or symptomatic or untreated CNS metastases.
8. Has other serious illness or medical condition, such as active infection, unresolved bowel obstruction, psychiatric disorders, or cerebrovascular accident (within 1 year of study entry).
9. Has known history of Human Immunodeficiency Virus (HIV) (HIV 1/2 antibodies). HIV 1/2 antibodies testing is only required when the investigator has reason to suspect the patient has Human Immunodeficiency Virus infection.
10. Has known active Hepatitis B (e.g. HBsAg reactive) or Hepatitis C (e.g. HCV RNA [qualitative] is detected). Hepatitis B surface Antigen reactive testing and HCV RNA [qualitative] testing is only required when the investigator has reason to suspect the patient has Hepatitis B infection or Hepatitis C infection.
11. Has received high dose chemotherapy followed by autologous stem cell transplantation less than 90 days prior to first dose of MK-8628.
12. Has concomitant (and cannot discontinue) therapy with strong CYP3A4 or CYP2A6 interfering drugs, or any other medication / therapy prohibited by the protocol. Please see Section 5.5 .
13. Has peripheral cytopenia (i.e. auto-immune hemolytic anemia or thrombocytopenia).
14. Has acute promyelocytic leukemia or clinically uncontrolled (i.e. with bleeding) disseminated intravascular coagulation (DIC).
15. Has chronic graft versus host disease (GVHD) or on immunosuppressive therapy for the control of GVHD.

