### **Prohibited**

Listed below are specific restrictions for concomitant medications / therapy during the course of the trial:

1. Concurrent treatment with any investigational drug or anticancer (antineoplastic) therapy, including the following: chemotherapy, immunotherapy, hormone therapy, or biological therapies.

*(The only exception is hydroxyurea given to control hyperleukocytosis that can be continued until 48 hours before MK-8268 treatment initiation, but must be stopped at that time. Furthermore, should a rapidly increasing white blood cell count occur during the first cycle of MK-8268 treatment, hydroxyurea should not be given earlier than day cycle 1 / day 3, nor beyond day 43 (cycle 3 / day 1), and for the shortest period possible as clinically indicated to control hyperleukocytosis and maintain the subject on study. On day 43 (cycle 3 / day 1), the decision to start MK-8268 for cycle 3 will be made by the investigator according to the subject's anticipated benefit. If hydroxyurea has to be resumed during cycle 3, this will be considered as MK-8268 treatment failure, and the subject will be withdrawn from the study)*

2. Corticosteroids (except chronic treatment with  $\leq$  4.0 to 6.0 mg / day of methylprednisolone or equivalent dose of other corticosteroids).
3. Prophylactic antiemetic drugs or other drugs given with a prophylactic intent in the first cycle (unless the Early Phase Safety Teleconferences Meeting decides to deliver systematic premedication).
4. Strong inducers, strong inhibitors, and sensitive / narrow therapeutic range substrates of the P450 cytochrome enzymes CYP3A4 and CYP2A6 (see Section 12.9) are prohibited. Moderate inducers and moderate inhibitors of these cytochrome enzymes should be used with caution. Since this list is not comprehensive, the investigator should use his/her medical judgment when a subject presents with a medication not on the list or call the Sponsor Clinical Director for clarification.

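### Appendix 12.9 states and marks a narrower set of prohibited CYP drugs than Section 5.5.1 item 4, and leaves the status of three dual-listed drugs and of the CYP2A6 lists unclear

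*Combined protocol and SAP*

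**What the plan says.** Section 5.5.1, Prohibited, item 4, gives the rule in the main text: "Strong inducers, strong inhibitors, and sensitive / narrow therapeutic range substrates of the P450 cytochrome enzymes CYP3A4 and CYP2A6 (see Section 12.9) are prohibited". It continues: "Moderate inducers and moderate inhibitors of these cytochrome enzymes should be used with caution". For gaps it adds that "the investigator should use his/her medical judgment when a subject presents with a medication not on the list", or the Sponsor Clinical Director may be called.

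Appendix 12.9 opens with its only statement of prohibition: "Strong CYP3A4 interfering agents are prohibited (in bold and underlined". It then defines a strong inhibitor and a strong inducer by their effect on the AUC or clearance of a substrate, and tabulates the drugs. The table has columns for strong and moderate CYP3A4 inducers and inhibitors, for sensitive and narrow-range CYP3A substrates, and for CYP2A6 inducers, inhibitors and substrates.

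Section 4.1.1.2 says that several enzymes metabolise MK-8628, which lessens the worry about other drugs changing its levels. Its inhibition of CYP2A6 and CYP3A4, in contrast, "raises concerns that MK-8628 could be a perpetrator in a DDI with co-administered drugs whose clearance is primarily mediated by these enzymes".

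Exclusion criterion 12 in Section 5.1.3 bars a subject who "Has concomitant (and cannot discontinue) therapy with strong CYP3A4 or CYP2A6 interfering drugs". It then adds any other medication that the protocol prohibits and refers to Section 5.5.

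**The concern.** A site checking a subject's medication will probably go to the list, because 5.5.1 sends it there. The list has a marking key. The key tags one class that 5.5.1 prohibits (strong CYP3A4 agents) and leaves another untagged (the substrates). A reader who trusts the key may take an untagged drug as permitted.

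The untagged class is the one that Section 4.1.1.2 singles out. The appendix marks drugs that could alter MK-8628 and does not mark drugs that MK-8628 could alter.

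Two further gaps do not depend on the marking. Some drugs fall in two classes with different status under 5.5.1, and the CYP2A6 lists lack the grades that the 5.5.1 rule needs. At stake is whether a safety rule facing the sites can be applied in the same way everywhere.

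**Working it through.** No sample size, error rate or event count is involved, so the check compares the passages and counts the lists in 12.9 as they appear in the text.

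**Step 1: the two rules side by side.**

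| Class | Section 5.5.1 item 4 | Appendix 12.9 |
|---|---|---|
| Strong CYP3A4 inducers and inhibitors | prohibited | prohibited, underlined |
| Moderate CYP3A4 inducers and inhibitors | caution | listed, no status given |
| Sensitive or narrow-range CYP3A substrates | prohibited | listed, no status given, not underlined |
| CYP2A6 agents and substrates | prohibited if strong, or if a sensitive or narrow-range substrate | listed without grades, no status given |

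**Step 2: substrates prohibited by 5.5.1 but not marked in 12.9.**
- Sensitive CYP3A substrates: 8 + 8 + 8 + 6 = 30.
- Narrow-range CYP3A substrates: 6 + 6 = 12.
- In both lists: alfentanil and sirolimus, so 2.
- Distinct substrates: 30 + 12 − 2 = 40.
- Also in the underlined strong-inhibitor columns: conivaptan, indinavir, lopinavir, saquinavir and tipranavir, so 5. These agree in both places.
- Remaining: 40 − 5 = 35, that is 35/40 = 87.5% of the listed substrates.

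**Step 3: drugs in two classes with different status.**
- Moderate CYP3A4 agents: 12 inducers + 16 inhibitors = 28.
- Moderate agents that are also among the 40 substrates: aprepitant and darunavir (under "Moderate CYP3A4 inhibitors" and under "CYP3A Sensitive substrates"), and cyclosporine (moderate inhibitor and narrow-range substrate). That is 3.
- No drug is both strong and moderate for CYP3A4.
- The judgment clause in 5.5.1 does not settle these three, because it covers drugs that are not on the list.

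**Step 4: CYP2A6.**
- The lists hold 2 inducers, 7 inhibitors and 7 substrates. SM-12502 and valproic acid are in two of them, so the distinct entries are 2 + 7 + 7 − 2 = 14.
- Three (rifampicin, grapefruit juice and ketoconazole) also stand in the underlined strong CYP3A4 columns. The other 14 − 3 = 11 have no marking anywhere in the table.
- None is graded strong or moderate, and no substrate is labelled sensitive or narrow-range.
- Phenobarbital is a moderate CYP3A4 inducer (caution) and an ungraded CYP2A6 inducer, so its status cannot be read off.

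**Step 5: effect on statistical quantities.** The dose-decision table (Table 4), the interval table (Table 11) and the sample size do not use these lists. None of them changes.

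**The case against.** The strongest case on the other side is that 5.5.1 is the operative rule and 12.9 is a look-up table. The appendix has columns headed with the very substrate classes that 5.5.1 names. A reader might infer that 12.9 says only strong CYP3A4 agents are prohibited, but that word is not there. The sentence can be read as a key to the marking, which makes 12.9 an incomplete restatement and not a contrary rule. This stands, and it is why the point is one of ambiguity. It does not remove the problem, because a key that tags one prohibited class and not another can mislead.

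On the three drugs, it can be argued that caution for one property does not cancel prohibition for another, so applying both sentences gives prohibition. That is a coherent reading, but 5.5.1 does not state it.

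On CYP2A6, the definitions of strong in 12.9 are worded for any CYP enzyme, so the term has a meaning there. The appendix still does not say which CYP2A6 entries meet it, and it defines neither sensitive nor narrow-range.

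The formatting caveat also stands in part. The header promises bold and underlining, and only underlining survives in the extracted text, so some marking may be lost. The wording of the sentence does not depend on formatting and covers strong CYP3A4 agents alone.

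Other rules narrow the practical reach. Section 5.5.1 separately bars concurrent anticancer drugs (dasatinib is among the 35), limits corticosteroids and bars prophylactic antiemetics in the first cycle. Exclusion 15 bars immunosuppressive therapy for control of graft-versus-host disease. Section 5.5 requires agreement of investigator, Sponsor and subject on continuing trial therapy. The figure of 35 therefore counts mismatched entries. It is not a count of drugs that sites were free to use.

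**Conclusion.** The mismatch is real. Section 5.5.1 prohibits more than 12.9 states or marks: 35 of 40 distinct CYP3A substrates are affected, three drugs have two statuses with no stated precedence, and none of the 14 distinct CYP2A6 entries is graded. The counts rest on the lists as extracted. The reading of which drugs are marked rests on the underlining that survives.

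Three stronger readings are not supported. First, a reader might infer that sites will apply different rules. The documents show only that they may. Second, a reader might infer that exclusion 12 is also too narrow. It already takes in anything else the protocol prohibits and defers to Section 5.5. Third, a reader might infer that the DLT endpoint is biased through interaction events blamed on MK-8628. Section 4.1.1.2 reports IC50 values above 10 μM, with 30% (CYP2A6) and 39% (CYP3A4) inhibition at 10 μM. The documents do not quantify any resulting rise in substrate levels or link one to a DLT count.

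The Trial Summary says that enrollment has been discontinued and one subject remains. The present use of the correction is therefore that subject's co-medication and a clear record of the rule under which the data were collected. No view is taken here on which status is clinically right.

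**What to change.** Reconcile Section 5.5.1 item 4 and Appendix 12.9.

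- Give each list in 12.9 an explicit status, prohibited or caution, and reword its opening sentence to match 5.5.1. If the appendix reflects what the sponsor intends, amend 5.5.1 instead.
- State which status governs a drug listed in two classes, and apply that to aprepitant, darunavir and cyclosporine.
- State which CYP2A6 entries the rule covers, either by grading them or by naming them. Phenobarbital should be resolved in the same step.

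The sponsor decides which status applies. Exclusion 12 needs no substantive change. The cost is a text edit in two places, with no new procedures, data or analyses.
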